7.2 ANALYSIS OF SECONDARY RESPONSE ENDPOINTS

Descriptive Statistics (n, mean, SD, Qtr1, median, Qtr3 and CV) will be provided, by product, for the following measurements:

- Exhaled breath sessions
 - Cartridge weight change by sampling session and overall
- 12 hour ad-libitum use session
 - Cartridge weight change by cartridge and overall (Template provided)
 - Total cartridge weight change (Template provided)
 - Number of cartridges used
 - Puff count by cartridge and overall
 - Total puff count
 - Average puff duration by cartridge and overall
 - Total puff duration by cartridge and overall
 - Average puff duration of the total puffs
 - Total puff duration
- Complete cartridge use over 12-hour ad-libitum use session
 - Puff count per complete cartridge (Template provided)
 - Average puff duration per complete cartridge
 - Total puff duration per complete cartridge
 - Cartridge weight change per complete cartridge

Definition of complete cartridge use: If a subject replaced a cartridge with a new cartridge, the previous cartridge is considered a complete cartridge. If subject only used one cartridge for the day, none would be counted as complete cartridge.

Mixed models will be applied to the following measurements:

- Total puff count over the 12-hour ad-libitum use session

Statistical Analysis Plan

- Total puff duration over the 12-hour ad-lib use session
- Average puff duration of the total puffs over the 12-hour ad-lib use session
- Total cartridge weight change over the 12-hour ad-lib use session
- Cartridge weight change calculated in each exhaled breath sampling session

Each model will include fixed effect terms for product, period and sequence. Subjects within sequence will be modeled as random effects. Models will be fit with SAS Proc Mixed, using the procedures described in Section 7.1.

7.3 EVALUATION OF SAFETY PARAMETERS

All safety analyses will be performed on the safety analysis set. Safety data, presented by test product, will be summarized on an “as-treated” basis using descriptive statistics (e.g., n, mean, standard deviation, median, minimum, maximum for continuous variables; n [%] for categorical variables). Safety variables will include test product use-emergent adverse events (PEAEs), and vital signs.

7.4 ADVERSE EVENTS

All AE data for the safety population will be coded (to the lowest-level term) by using the Medical Dictionary for Regulatory Activities (MedDRA, Version 17.1). AEs will be listed in by-subject data listings, including verbatim term (investigator terms from the case report form), preferred term, test product, severity, and relationship to test product. Summary tables of frequency counts of AEs will be provided by primary system organ class (SOC), preferred term, and test product. Frequency counts of AEs will also be summarized by severity and relationship to test product and overall.

A PEAE is defined as an adverse event that:

- Emerges during exposure to a test product, having been absent previously, or:
- Worsens in severity during sessions within visits 2, when the adverse event is continuous in duration.

The incidence (%) will be determined by calculating the number of subjects with at least 1 event and the percentage of subjects with PEAEs by preferred term. The

Statistical Analysis Plan

incidence of PEAEs will be reported as the number (percentage) of subjects with PEAEs by SOC and preferred term. A subject will be counted only once within a SOC and preferred term, even if the subject experiences more than one PEAE within a specific SOC and preferred term. A missing or unknown value for the assessment will be considered worst. The number (percentage) of subjects with PEAEs will also be summarized by maximum severity (mild, moderate, or severe). If a given subject had more than one PEAE mapped to the same PT, then that PEAE will be represented according to the corresponding maximal level of severity.

The number (percentage) of subjects with PEAEs will also be summarized by relationship to test product. If a given subject had more than one PEAE mapped to the same PT, then that PEAE will be represented according to the strongest relationship to study product. Test product-related PEAEs include those adverse events considered by the investigator to be “definitely”, “possibly”, “probably”, “unlikely”, or “not” related to test product usage. The number (percentage) of subjects with test product-related PEAEs will also be summarized by maximum severity (mild, moderate, or severe).

The number (percentage) of subjects with serious adverse events (SAEs) will be summarized by MedDRA, SOC, and preferred term for each test product group. A subject data listing of all SAEs will be provided.

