1.2.2.3 Ambulatory Studies

In addition, ALCS sponsored an ambulatory vaping exposure study (COV-M10-01-14) in 2014. One hundred forty-eight (70 males) healthy adult smokers were enrolled in the randomized control study. One hundred and three (48 males) subjects were allowed to smoke their own brand conventional cigarettes and use an e-vapor CVR1.5 (1.5% tobacco-derived NBW, either Classic or Menthol flavored) product ad libitum and 45 (22 males) subjects smoked their conventional cigarettes ad libitum without using EVPs for 4 weeks. Of the 103 subjects assigned to the e-vapor group, 34 reported 44 AEs, and 9 of the 45 subjects assigned to the smoking group reported 13 AEs. Out of the 44 AE reports from the subjects assigned to the CVR1.5 e-vapor group, 4 mild AEs were considered to be possibly related to the Test Products by the investigators (2 upper respiratory tract infection, 1 throat irritation, and 1 headache).

Altria Client Services LLC also sponsored an ambulatory tobacco product use study (ALCS-M10-02-14). Two hundred twenty-six (104 males) adult cigarette smokers were randomized into 5 groups investigating the use of cigarettes with the use of CVR1.5 EVPs (1.5% tobacco-derived NBW in Classic [C15] or Menthol [M15] flavor and 2.5% tobacco-derived NBW in Classic [C25] or Menthol [M25] flavor) for 3 weeks. Two groups were instructed to use their own brand cigarettes and CVR1.5 EVPs (n=51, C15/M15; n=49, C25/M25) ad libitum and 2 groups were instructed to use their own brand cigarettes ad libitum and at least 1 CVR1.5 e-vapor cartridge per day (n=52, C15/M15; n=49, C25/M25). The control group (n=25) continued to smoke their own brand cigarettes ad libitum. A total of 26 subjects (11.5% of enrolled subjects) reported 37 post-randomization AEs (1 post-randomization serious AE [SAE] occurred in the control group and was not related to Test Product). In the 201 subjects randomized to CVR1.5 EVP use groups, 15 mild or moderate AEs from 9 subjects (4% of CVR1.5 e-vapor use groups) were considered as unlikely, possibly,

or likely related to the Test Products by the investigators (no definitely related AEs were reported). Of these 15 unlikely, possibly, or likely related AEs, the only AE reported by more than 1 subject across all of the CVR1.5 use groups was mild oral discomfort (2 subjects; 1% of the CVR1.5 e-vapor use groups).

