8.0 Adverse Event Guidelines

8.1 Adverse Events

The following is the definition of an **AE**:

Any unfavorable and unintended sign (including an abnormal laboratory finding^a), symptom, or disease^b temporally associated with the use of a study product, **whether or not** related to the study product.^{12,13}

^a For this study, a laboratory AE is defined as an abnormal laboratory finding that is determined by the investigator to be clinically significant for that subject.

^b This includes a newly developed, worsened preexisting, recurring intermittent or intercurrent illness, injury, or condition.

All AEs occurring during this clinical trial after the subject has signed the ICF must be recorded in the CRF, including the date and time of onset and outcome of each event. Any condition existing prior to the use of a study product will be documented as a concomitant disease or condition and should be reviewed to determine whether or not the subject meets the inclusion and exclusion criteria.

Surgical procedures themselves are not AEs; they are therapeutic measures for conditions that require surgery. The condition for which the surgery is required may be an AE.

No causal relationship with the study products or with the clinical study itself is implied by the use of the term “adverse event.”

The investigator will review each event and rate each reported sign or symptom on a 3-point severity scale. The following definitions for **rating severity**¹³ will be used:

Mild: The AE is easily tolerated and does not interfere with daily activity.

Moderate: The AE interferes with daily activity, but the subject is still able to function.

Severe: The AE is incapacitating and requires medical intervention. Note: This is not the same as “serious,” which is based on the outcome or action criteria usually associated with events that pose a threat to life or functioning.

Each AE will also be assessed by the investigator for **relationship to study product (causality)** using the following grades of certainty^{14,15} (the strength of a causal association may be revised as more information becomes available):

Not related: Clearly and definitely due to extraneous cause (eg, disease, environment).

Unlikely:

- a. Does not follow a probable temporal (ie, time) sequence from use of study product.
- b. Does not follow a known pattern of response to the study product.

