- c. Could plausibly have been produced by the subject’s clinical state/underlying disease or other drugs or chemicals the subject received.
- d. Does not reappear or worsen when the study product is re-administered.

Possible:

- a. Follows a reasonable temporal (ie, time) sequence from use of study product.
- b. Follows a known pattern of response to the study product.
- c. Could also have been produced by the subject’s clinical state/concurrent disease or other drugs or chemicals the subject received.

Likely:

- a. Follows a reasonable temporal (ie, time) sequence from use of study product.

- b. Follows a known pattern of response to the study product.
- c. Could not readily have been produced by the subject's clinical state/concurrent disease or other drugs or chemicals.
- d. Follows a clinically reasonable response on withdrawal (dechallenge) (ie, disappears or decreases when the study product is stopped or reduced).
- e. Rechallenge information is **not** required to fulfill this definition.

- Definitely:
- a. Follows a reasonable temporal (ie, time) sequence from use of study product.
 - b. Follows a known pattern of response to the study product.
 - c. Cannot be explained by the subject's clinical state/concurrent disease or other drugs or chemicals.
 - d. Follows a clinically reasonable response on withdrawal (dechallenge) (ie, disappears or decreases when the study product is stopped or reduced).
 - e. Recurs with re-exposure to study product (rechallenge). Note: Re-exposure of the subject is NOT required, but the "certainly/definitely related" category may only be used when recurrence is observed.

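### SAP 7.4 counts adverse events judged not related as test product-related, so the related-event severity table is mislabelled and at best repeats the all-event table

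*SAP*

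**What the plan says.** Protocol 8.1 has the investigator grade each adverse event for causality on five levels: *Not related*, *Unlikely*, *Possible*, *Likely*, *Definitely*. The lowest is defined as "Not related: Clearly and definitely due to extraneous cause". For *Likely*, one criterion is that the event "Could not readily have been produced by the" subject's own condition or other drugs or chemicals. The protocol defines no pooled related class. Its section 9.6 asks for adverse event counts by severity and by relationship, with no formal tests on safety data.

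SAP 7.4 plans three PEAE summaries that matter here:

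- All PEAEs by severity: "The number (percentage) of subjects with PEAEs will also be summarized by maximum severity (mild, moderate, or severe").
- PEAEs by relationship, where several events under one preferred term are collapsed: "then that PEAE will be represented according to the strongest relationship to study product".
- Related PEAEs by severity: "The number (percentage) of subjects with test product-related PEAEs will also be summarized by maximum severity".

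The sentence just before the third summary supplies the only definition of its key term: "Test product-related PEAEs include those adverse events considered by the investigator to be “definitely”, “possibly”, “probably”, “unlikely”, or “not” related to test product usage".

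**The concern.** An event the investigator attributes to an extraneous cause is, under this definition, a test product-related event. The next planned table takes its population from that definition, so its title would promise a subset that its contents do not deliver. A reader who takes the title at face value would attribute every PEAE to the product, including those judged unrelated.

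There is also a labelling mismatch. The SAP list contains *probably*, which is not a protocol grade, and lacks *Likely*, which is. A programmer has to guess the mapping. The by-relationship summary is exposed as well, because choosing the strongest relationship needs an ordered scale and the SAP never states one. Its list puts *possibly* before *probably*, so list order cannot serve as the ranking if *probably* means *Likely*.

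**Working it through.** The plan gives no figure on this point, so there is none to reproduce. The check compares the two sets of grades and follows the result into the tables.

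**1. Matching the grades**

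| Protocol 8.1 | SAP 7.4 list |
|---|---|
| Definitely | definitely |
| Likely | probably (by synonym only) |
| Possible | possibly |
| Unlikely | unlikely |
| Not related | not |

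**2. Consequence of each reading**

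- *Reading A: probably means Likely.* All 5 of 5 grades are in the related set, so related PEAEs are simply all PEAEs. SAP 7.4 also treats a missing or unknown assessment as the worst value; if that rule covers causality, a missing grade does not remove an event from the related set. The two severity tables are then the same by identity. On 10,000 simulated data sets of 32 subjects with a causality grade on every event, they agreed 10,000 times, as they must.
- *Reading B: the words taken literally and as a complete list.* *Likely* has no entry, so 4 of 5 protocol grades are related: the related set omits *Likely* and keeps *Not related*. The table is no longer a copy but a wrong subset.

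**3. Small worked example (invented data)**

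Five subjects have one PEAE each: not related and severe; unlikely and mild; possible and mild; likely and moderate; definitely and mild.

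| Rule for related | Mild | Moderate | Severe |
|---|---|---|---|
| All PEAEs | 3 | 1 | 1 |
| SAP, reading A | 3 | 1 | 1 |
| SAP, reading B | 3 | 0 | 1 |
| *Not related* excluded | 3 | 1 | 0 |
| *Not related* and *Unlikely* excluded | 2 | 1 | 0 |

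Under both readings of the SAP, the one severe event appears as product-related although the investigator judged it unrelated.

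**4. Illustration from the protocol's own background**

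Protocol 1.2.2.3 describes a 4-week ambulatory study with 103 subjects in the e-vapor group, 34 of whom reported 44 adverse events. It reports: "Out of the 44 AE reports from the subjects assigned to the CVR1.5 e-vapor group, 4 mild AEs were considered to be possibly related".

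- Under the SAP wording (reading A): 34/103 = 33.0% of subjects with a related event.
- On the cut reported there, 4 events fall in 1 to 4 subjects: 1/103 = 1.0% to 4/103 = 3.9%.
- Ratio at its smallest: 34/4 = 8.5.
- By event: 44/44 = 100% against 4/44 = 9.1%.

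This assumes that all 44 events would count as product-emergent and that the 4 listed are all those graded at least possible.

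**5. Where *Unlikely* belongs**

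The documents do not settle this. The study above is summarised by events judged possibly related. The second ambulatory study in the same section pools a wider group: "Of these 15 unlikely, possibly, or likely related AEs, the only AE reported by more than 1 subject". Neither summary counts events judged not related.

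**The case against.** The best defence is that the sentence is a drafting slip. It sits in the paragraph on the by-relationship summary, straight after the strongest-relationship rule, and may have been meant only to list that table's categories. That is plausible. It does not repair the text, because the next sentence uses the same term to define a table. If the sentence is only a list, that table has no definition, and the cut would be chosen later in an open-label study, possibly with the events in view.

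A second point is weight. The protocol does not ask for this table, safety is descriptive, no primary or secondary objective uses relatedness, and the listings and by-relationship summaries let a reader recover the grades. Under reading A the error over-attributes events and hides none. All of this stands, and it limits the importance of the point.

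Third, the numerical illustration is borrowed. It comes from smokers who used a different product alongside their own cigarettes for four weeks, not from e-vapor users confined for a few days. The in-clinic studies in the protocol look different: in one, 5 of 24 subjects had events judged likely related; in another, no adverse events were reported. The 8.5-fold ratio therefore shows the direction and a possible scale, and does not predict this trial's result.

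Finally, any default for *Unlikely* is a choice the documents do not dictate. That is correct, and the fix leaves it open to the sponsor.

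**Conclusion.** The concern holds. As written, the SAP places events judged not related in the related group and builds a table on that definition; nothing elsewhere in the SAP or protocol narrows it. At best (reading A) the table is a relabelled copy of the all-PEAE severity table; at worst (reading B) it also loses the events of likely causality. The conclusion that *Not related* is misplaced rests on the wording alone and needs no assumption about intent. The exact-duplicate result needs *probably* to mean *Likely* and, where a causality grade is missing, the worst-value rule to apply to causality.

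The size is one planned descriptive table. How far it would mislead in this trial depends on event counts that the documents do not give. It should be corrected before tables are programmed, but it does not touch the primary or secondary analyses.

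**What to change.** Replace the defining sentence in SAP 7.4 with:

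> Relationship is reported on the protocol Section 8.1 scale, in increasing order: Not related, Unlikely, Possible, Likely, Definitely. Test product-related PEAEs are those graded Possible, Likely or Definitely.

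If the sponsor prefers to pool *Unlikely* with the related grades, as for one earlier study, the SAP should say so now. In either case *Not related* stays outside. The stated order also gives the strongest-relationship rule the ranking it needs. The PEAE definition itself does not change.

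The cost is one sentence before programming, with no new data. The downside is that leaving *Unlikely* out gives a lower, less conservative related count than the wider pooling, and one not directly comparable with that earlier study's summary.

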7.5 PRIOR AND CONCOMITANT MEDICATIONS

Prior and current medication information is collected at the screening assessment. Concomitant medication data are collected from baseline (Visit 2, Day 1) through the follow-up assessment. Prior medications will be listed by subject. A separate listing of concomitant medications will be made, also by sequence and subject. For both listings, start and stop dates (and times for the 4 to 12-hour assessments) of each medication will be included.

All investigator terms for medications recorded in the eCRF will be coded to an 11-digit code using the World Health Organization Drug Dictionary WHO DDE Sept 2015 version.

If a medication has an end date and end time that occur before the product use date and time, that medication will be considered a prior medication. If a medication has a start

Statistical Analysis Plan

date and start time that occur before the product use date and time but an end date and end time that occur after the product use date and time, that medication will be considered prior and concomitant. If a medication has a start date, start time, end date, and end time that occur after the product use date and time, that medication will be considered concomitant. Should a missing start date, start time, end date, or end time lead to ambiguity in whether a medication is prior or concomitant, the medication will be considered concomitant.

7.6 VITAL SIGNS AND OTHER PHYSICAL EXAMINATIONS

Vital signs will be collected during screening (Visit 1) and at Visits 2, before subjects receive their first test product. Subjects' screening visit will be considered their baseline assessment. Vital sign measurements include pulse rate, respiratory rate, oral body temperature, and seated blood pressure (systolic and diastolic). These measurements will be listed by visit and subject. Vital sign values and change from baseline values will be computed for each vital sign and summarized by visit.

Incidence of potentially clinically significant results in vital signs will be provided from the AE summary tables, if applicable.

Statistical Analysis Plan

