1.2.4 Product Warnings

The adult subjects will be informed that the EVPs used in this research bear the following warning:

WARNING: This product is not a smoking-cessation product and has not been tested as such. This product is intended for use by persons of legal age or older, and not by children, women who are pregnant or breastfeeding, or persons with or at risk of heart disease, high blood pressure, diabetes, or taking medicine for depression or asthma. Nicotine is addictive and habit forming, and it is very toxic by inhalation, in contact with the skin, or if swallowed. Nicotine can increase your heart rate and blood pressure and cause dizziness, nausea, and stomach pain. Inhalation of this product may aggravate existing respiratory conditions. Ingestion of the nonvaporized concentrated ingredients in the cartridges can be poisonous.

For products sold in the State of California, the following warning will be present at points of sale:

CA Proposition 65 **WARNING:** This product can expose you to chemicals including glycidol, which is known to the State of California to cause cancer, and nicotine, which is known to the State of California to cause birth defects or other reproductive harm. For more information, go to www.P65Warnings.ca.gov.

Glycidol is detected in the aerosols generated from ALCS's products. International Agency for Research on Cancer has classified glycidol as "probably carcinogenic to humans (Group 2A)"

(http://monographs.iarc.fr/ENG/Classification/latest_classif.php). ALCS's scientific test data, however, show that the anticipated human exposures are substantially below the established regulatory limits

(https://www.osha.gov/dts/chemicalsampling/data/CH_243700.html).

In summary, as stated in section 1.2.1, based on the totality of evidence including the individual material assessment, literature review, and collective in vitro and in vivo testing, we believe there is no concern for use of the test products in this clinical study. All four formulations being used in this study are currently available in the commercial market (since 8 August 2016).

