5.0 Study Conduct

5.1 Procedures by Visit/Day

5.1.1 Visit 1 (Screening)

The following screening procedures will be completed within 30 days of subject enrollment:

- Verify age and identity with government-issued identification
- Explain study procedures and obtain signature on the informed consent form
- Review inclusion and exclusion criteria
- Document demographics (Demographics Questionnaire)
- Document tobacco/nicotine product-use history (Tobacco/Nicotine Product Use-History Questionnaire)
- Record medical history
- Measure vital signs
- Measure height, weight, and BMI
- Collect blood sample for clinical chemistry (at least 8 hours fasting), hematology (at least 8 hours fasting), serology, and serum pregnancy (all females only) tests
- Follicle-stimulating hormone test for postmenopausal females only
- Collect urine sample for urinalysis, drug and alcohol screening, and cotinine screening (exhaled breath test for alcohol is also acceptable)
- Review concomitant medications and AEs
- Electrocardiogram
- Physical examination
- Provide tobacco cessation information (Quit Assist™ website referral)

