5.1.2 Visit 2: Day -1 Check-in

Subjects will return to the clinic for their second visit on Day -1, and the following procedures will be completed:

- Review inclusion and exclusion criteria
- Measure vital signs
- Collect urine sample for urine drug and alcohol screening (exhaled breath test for alcohol is also acceptable), urine pregnancy test (all females only)
- Product trial
 1. Subjects will use the products in an assigned order (A, B, C, D)

2. Subject will engage in brief product trial with each e-vapor product (i.e., ad libitum use for 10 minutes).
3. Trials of each e-vapor product will be separated by approximately 30 minutes (from the end of each product trial).
- Review concomitant medications and AEs
- Remind subjects of study restrictions

5.1.3 Visit 2: Day 1 through Day 4

Subjects will abstain from tobacco or nicotine use overnight and repeat the following procedures on Days 1, 2, 3 and 4:

- Measure vital signs
- Subjects will be randomly assigned to a product use schedule (section 5.3)
- Exhaled breath product-use session (1 test product per day for 4 days per randomization schedule)
 1. 10 sham puffs (empty cartridge and inactive battery)
 - 5-second puff duration, one puff every 30 seconds for 5 minutes (Note: All exhaled breath will be captured after the first puff to ~60 seconds after the last puff in Trapping Container 1 with a nose clip in place.) All puff durations will be documented.
 - Subjects will be instructed to inhale as they normally use EVPs and not to only mouth puff.
 - Subjects will also be instructed to make every attempt to exhale directly into the collection device and minimize leakage of the exhaled vapor in the ambient air.
 2. 10 puffs with assigned test product with fully charged standard battery (BVR2.3)
 - 5-second puff duration, one puff every 30 seconds for 5 minutes (Note: All exhaled breath will be captured after the first puff to ~60 seconds after the last puff in Trapping Container 1 with a nose clip in place.) All puff durations will be documented.
 - Subjects will be instructed to inhale the vapor as they normally use EVPs and not to only mouth puff.
 - Subjects will also be instructed to make every attempt to exhale directly into the collection device and minimize leakage of the exhaled vapor in the ambient air.
 3. At least 45 minutes without any tobacco or nicotine use

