5.2.12 Vital Signs

Vital signs (respiratory rate, pulse rate, blood pressure, and oral temperature) will be assessed with subjects in the sitting position after at least 5 minutes of rest and at least 15 minutes after last tobacco use.

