1.4 DEFINITION OF THE BASELINE ASSESSMENT

Data collected at the screening visit (e.g., vital signs; Visit 1), will be considered to be baseline values. For primary responses collected from a subject only during Visit 2 the sham concentrations of the each analyte, in a given period, will be considered the baseline (i.e., pre-test product use) concentration of each analyte for that subject, in that period. The sham analyte means will be used to compute test product post-use minus pre-use differences (= sham-corrected amount = SCA) of each of the 7 analyte concentrations of each subject, in each period.

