- Trapping Container 1: captures nicotine, glycerin, propylene glycol, and menthol
- Trapping Container 2: captures formaldehyde, acetaldehyde, and acrolein
- Test product cartridges will be weighed before and after each collection.

Upon completion of the exhaled breath product use session, the subjects will be allowed to use new cartridges with freshly charged “BVR2.3 Rev 05 batteries with topography v1” batteries ad libitum for the next 12 hours following the package insert instructions. These batteries have been verified to perform within acceptance criteria of batteries without topography chip. Cartridges will be weighed before and after use. The “BVR2.3 Rev 05 battery with topography v1” will record all puffs and duration of puff during the 12 hours of ad libitum use. After the 12 hours of ad libitum use, subjects will complete the Use the Product Again Questionnaire.

After overnight tobacco and nicotine abstinence, the subjects will have vital signs recorded and repeat the exhaled breath test product use session and 12-hour ad libitum use session with their assigned test product on days 2 through 4 (1 test product per day). After each 12-hour ad libitum use session, subjects will complete the Use the Product Again Questionnaire.

Upon completion of the ad libitum product use session on Day 4, subjects will undergo end-of-study assessments and be released from the site.

The 4 test products are described in Section 1.3. The Schedule of Assessments (SOA) is provided in Table 3.

Statistical Analysis Plan

Table 3. Schedule of Assessments

EVENT	Visit 1 (Day -30 to Day -1)	Visit 2 (Day -1 Check-in)	Visit 2 (Day 1 through Day	End of Study
Age verification	X			
Informed consent	X			
Medical history	X			
Review of inclusion and exclusion criteria	X	X		
Demographics (including questionnaire)	X			
Tobacco and Nicotine Product-Use History Questionnaire				
Vital signs ¹	X	X	X	
Urine cotinine measurement	X			
HIV, HBsAg, anti-HCV screening	X			
Body weight, body height, and body mass index	X			
Clinical chemistry, hematology, and urinalysis	X			
Urine drug and alcohol screening ²	X	X		
Serum pregnancy test (all females only)	X			
Urine pregnancy test (all females only)		X		
FSH test (post-menopausal females only)	X			
Review of concomitant medications	X	X	X	X
Quit Assist™ Website Referral	X			X
Review of adverse events	X	X	X	X
Electrocardiogram	X			
Physical examination	X			X ³
Check-in procedures		X		
Confinement		X	X	
Product trial		X		

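### Vital-sign change on Days 1 to 4 is taken from a screening reading with recent nicotine use uncontrolled, so it mixes overnight abstinence, time and setting with any persisting effect; an abstinent Day 1 pre-session value is already collected.

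*SAP*

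**What the plan says.** The SAP fixes the baseline in two places that agree with each other. Section 1.4 reads "Data collected at the screening visit (e.g., vital signs; Visit 1), will be considered to be baseline values", and Section 7.6 repeats that the "screening visit will be considered their baseline assessment".

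On when screening happens and in what nicotine state, Protocol 5.1.1 says: "The following screening procedures will be completed within 30 days of subject enrollment". Protocol 5.2.12 requires vital signs to be taken seated, after 5 minutes of rest and "at least 15 minutes after last tobacco use". No longer abstinence is stated for screening.

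On the later readings, Protocol 5.1.3 says: "Subjects will abstain from tobacco or nicotine use overnight and repeat the following procedures on Days 1, 2, 3 and 4". The first procedure it lists is vital signs, ahead of the exhaled breath session. SAP 1.7 gives the same order for Days 2 to 4: "After overnight tobacco and nicotine abstinence, the subjects will have vital signs recorded and repeat the exhaled breath test product use session". A further reading is taken on arrival at Day -1 check-in. No vital signs are listed after product use on any day, or at end of study (Protocol Table 1 and 5.1.3.1).

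On reporting, Protocol 9.6 summarizes changes by test product and time point, with no formal tests. SAP 7.3 presents safety data by test product, but SAP 7.6 summarizes vital-sign changes by visit. SAP 7.6 also describes the timing as follows: "Vital signs will be collected during screening (Visit 1) and at Visits 2, before subjects receive their first test product".

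**The concern.** A change from baseline is easiest to read when both readings are taken under the same conditions. Here they are not. Participants are current nicotine users (urine cotinine of at least 500 ng/mL, e-vapor use on at least 4 of the past 7 days). At screening they may have used nicotine until 15 minutes before the reading; on Days 1 to 4 they have abstained overnight. The protocol's own product warning says "Nicotine can increase your heart rate and blood pressure", so losing that effect would be expected to lower pulse and blood pressure relative to screening.

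Vital signs are one of only two safety endpoints in SAP 3.3. With no tests planned, readers will rely on the tabulated mean changes. A fall caused by abstinence could look like a finding, or could offset a rise that persists into the next morning.

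The SAP handles the breath analytes differently: SAP 1.4 gives them a same-period pre-use baseline, the sham value. SAP 7.5 calls Visit 2, Day 1 the baseline for concomitant medications.

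**Working it through.** **Timing, from the documents' own figures**

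- Exhaled breath session: 4 collections x 5 min + 45 min rest = 65 min.
- Overnight gap: 24 h - 12 h ad libitum use - 65 min = 10 h 55 min. This reproduces the washout in SAP 1.3 exactly. It applies to the nights before Days 2 to 4; the documents give no length for the night before Day 1.
- Longest gap from screening: Day -30 to Day 1 is 30 days (no Day 0), and to Day 4 it is 33 days.

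**Conditions side by side**

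| Reading | Nicotine condition | Position relative to product use |
|---|---|---|
| Screening | at least 15 min since last use | up to 30 days before enrollment |
| Day -1 check-in | at least 15 min since last use | on arrival, before the product trials |
| Day 1 | overnight abstinence | before the first randomized session; after the Day -1 trials of all four products |
| Days 2 to 4 | overnight abstinence (10 h 55 min) | before that day's session |

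**Algebra**

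For one participant, let a be the shift due to overnight abstinence, t the shift due to time and setting, and r(d) any effect still present on the morning of day d. Apart from measurement error:

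- change from screening on day d = a + t + r(d), for d = 1 to 4;
- change from screening at check-in contains no a, since both readings fall under the 15-minute rule;
- change from Day 1 on day d = r(d) - r(1), for d = 2 to 4, if a and t are the same on each morning;
- difference between two days = r(d) - r(d'), whichever single baseline is used, because the baseline subtracts out within the participant.

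**Numerical check**

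The four-sequence design was simulated with 32 participants (4 sequences x 8), no product effect and t = 0. Assumed SDs were 6 units within and 10 units between participants. The values of a are assumptions.

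| Assumed a | Check-in minus screening | Days 1 to 4 minus screening | Days 2 to 4 minus Day 1 |
|---|---|---|---|
| 0 | 0.01 | 0.02 to 0.05 | -0.01 to 0.02 |
| -2 | 0.00 | -1.99 to -1.95 | -0.03 to -0.02 |
| -5 | -0.02 | -5.01 to -4.98 | -0.01 to 0.02 |
| -10 | 0.01 | -10.02 to -9.98 | -0.03 to 0.00 |

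The difference between products A and B was identical under the two baselines (largest discrepancy 0.0), with all four days kept for each participant.

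**Comparison with sampling error**

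The documents give no SD. For an assumed within-participant SD s, the standard error of a mean change is s x sqrt(2/32). For s = 4 this is 1.0 (95% half-width 1.96 x 1.0 = 1.96); for s = 10 it is 2.5 (1.96 x 2.5 = 4.9). An abstinence shift of 5 units would exceed the half-width across that range; a shift of 2 would do so only near its lower end.

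**The case against.** The strongest objection concerns what could be masked. A reader might infer that an acute rise in pulse or blood pressure from the products is being hidden. The schedule does not support that: every Day 1 to 4 reading precedes that day's use, so there is no on-product reading to distort. Only a residual effect on the following morning could be shifted. This stands in full.

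Four further limits also stand:

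- A reader might conclude that every change from baseline is affected. The Day -1 check-in reading precedes the overnight abstinence and falls under the same 15-minute rule as screening.
- Calling the screening visit non-abstinent goes beyond the text. Nicotine use there is uncontrolled, and some participants may not have used any recently.
- The size of the shift is unknown. The warning says only that nicotine can raise heart rate and blood pressure, so zero must stay in the range.
- Comparisons between products are unaffected, the safety analysis is descriptive, and SAP 7.6 also summarizes observed values.

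The alternative baseline has costs too. Day 1 itself gets no change value. If each morning reading is attributed to that day's product, each product loses the 8 of 32 participants who use it first. Day 1 also follows 10-minute trials of all four products. And if the SAP 7.6 timing sentence is read literally, so that readings after the first test product are excluded, no change from Day 1 could be computed.

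These points narrow the concern and shape the fix. None makes screening the better-matched comparator for the Day 1 to 4 mornings.

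**Conclusion.** The point holds for the absolute Day 1 to 4 changes. Each carries the full abstinence shift plus differences of time and setting. The protocol's warning makes a downward shift in pulse and blood pressure probable, on the assumption that some participants used nicotine near the screening reading. Over assumed shifts of 0 to -10 units the bias equals the shift. For example, a persisting next-morning rise of 5 units would be reported as 0 if the shift were -5, and as -5 if it were -10.

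The finding does not extend to acute effects, to the check-in change, to differences between products or to the primary analysis. It is a comparability flaw in the descriptive reporting of a named safety endpoint, worth correcting because the better-matched value is already scheduled. The gain from a Day 1 baseline assumes that the abstinence shift is about the same on all four mornings.

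**What to change.** In SAP 1.4 and 7.6:

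1. Define the vital-sign baseline for Visit 2 changes as the Day 1 morning value, after overnight abstinence and before the first randomized product session. Compute changes for Days 2 to 4.
2. Keep screening and check-in values for eligibility, observed-value summaries and listings.
3. Reword the SAP 7.6 timing sentence so that it plainly covers the Day 1 to 4 readings in Protocol 5.1.3.
4. Reconcile the by-visit summary in SAP 7.6 with SAP 7.3 and Protocol 9.6, and state to which product each morning reading is attributed. Under same-day attribution the reading precedes that day's use, and the product used first has no change value. Under previous-day attribution the Day 4 product has no following reading.
5. State that any descriptive product comparison uses observed values over all four days. The cancellation shown above relies on all four days being kept, and need not hold for raw product means of the Day 2 to 4 changes.
6. State that vital signs are all pre-session and are not intended to show acute effects.

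The cost is a few sentences of SAP text and revised table shells, with no new measurements. The price in information is the missing Day 1 change and a baseline that is free of randomized use but not of the Day -1 trials.
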